6.7. Safety

6.7.1. Extent of Exposure

A listing of treatment exposure data including planned dose and actual dose will be presented for the SafAS.

A summary of exposure will be presented for the SafAS. To this end, the number and percentage of participants dosed (0.5 mL, 1 mL) according to weight will be given. Moreover, the number and percentage of participants receiving the full dose will be calculated.

Total counts and percentages of participants will be presented for the categorical variables of:

- Infants dosed in season (dosed on or after the start date of RSV season)
- Infants dosed before the start of the RSV season

Exposure table and listing will also be produced in UK reconsented participants at the time of Second Year Analysis.

6.7.2. Adverse Events

6.7.2.1. Definitions/ Derivations

All AEs recorded on the eCRF will be coded using the MedDRA dictionary (version 25.0) and classified as treatment-emergent AEs (TEAEs) as follows:

- Pre-treatment AEs are events
 - that start prior to the start of the Treatment Period and with a stop date before the Treatment Period
- or
- with a stop date after the start of the Treatment Period or with a missing stop date, but with a grade lower or equal to 1.
- TEAEs are either events
 - with the start date and time posterior to the start of the Treatment Period and up to the end of the Treatment Period

or

- events with the start date and time prior to the start of the Treatment Period
 - whose severity is greater than 1 or missing
- and
 - stop date is missing or not before the Treatment Period.
- Treatment-Emergent Serious AEs will be defined as TEAEs where Serious = “Yes”
- The relationship between a TEAE and treatment is assessed as related, or not related. A treatment-related TEAE will be defined as a TEAE considered by the investigator as related or, with unknown / missing relationship to treatment for participants who received nirsevimab on Day 1. An unknown / missing relationship between a TEAE and treatment for participants who received no intervention will be considered as not related.
- Assessment of AE intensity will be based on the AEs intensity grading scales adapted from the “FDA Guidance for Industry: Toxicity Grading Scale for Healthy Adult and Adolescent Volunteers Enrolled in Preventive Vaccine Clinical Trials, September 2007”
- TEAEs leading to discontinuation of study are defined as TEAEs where “Caused Study Discontinuation” is indicated as “Yes”.
- Pyrexia includes those adverse events with PT term equal to ‘Pyrexia’.
- Injection site reactions include those adverse events with category of adverse event equal to ‘IMP Injection/Administration Site Reaction’ or ‘Other Vaccination Injection/Administration Site Reaction’.
- Rash includes those adverse events with PT term equal to ‘Erythema’, ‘Rash’, ‘Rash macular’, ‘Rash maculo-papular’ or ‘Urticaria’.

In addition to the aforementioned AE types, TEAEs of special interest will be identified in eCRF (Is the event an AESI = Yes):

- Hypersensitivity, including anaphylaxis
- Immune complex disease
- Thrombocytopenia

Immediate AEs are recorded to capture medically relevant AEs which occur within the first 30 minutes after immunization.

Medically Attended AE (MAAE) is a new onset or a worsening of a condition that prompts the participant or participant’s parent/legally acceptable representative to seek unplanned medical advice at a physician’s office or Emergency Department. Physician contact made over the phone or by e-mail will be considered a physician office visit for the purpose of MAAE collection. This includes medical advice seeking during the study visit or routine

medical care. This definition excludes pediatric check-ups, and follow-up visits for chronic conditions with an onset prior to entry into the study.

MAAE is derived in the CRF as “No” if :

- ✓ “None” or “Medication” is checked for Action Taken with Adverse Event item and
- ✓ “Health Care Provider Contact” or “Hospitalized” is checked.

Otherwise MAAE is derived as “Yes” in the CRF.

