8.3.2 Time Period and Frequency for Collecting AE and SAE Information

Immediate Post-immunization Observation Period

Participants enrolled in the nirsevimab group will be kept under observation for 30 minutes after immunization to ensure their safety. The post-immunization observation should be documented in the source document.

Non-serious Adverse Events

Non-serious adverse events will be collected from dosing/randomization (D01) until 30 days after immunization, ie, D31.

The intensity grading scale for non-serious adverse events is presented in Appendix 10.2.5.1.

Medically Attended Adverse Events (MAAEs)

MAAEs will be collected from dosing/randomization (D01) to D366 phone call.

Adverse Events of Special Interest (AESIs)

AESIs will be collected from dosing/randomization (D01) to D366 phone call

See Section 8.3.7 for the list of AESIs.

SAEs

Information on SAEs will be collected and assessed throughout the study, from dosing/randomization (D01) until 12 months after immunization (D366) for all participants.

Information on related SAEs will be collected and assessed from D366 until D731 post-dosing/randomization for UK reconsented participants. Refer to Section 8.3.1 for the exemption of reporting LRTI hospitalizations as SAEs.

It is to be noted that, since this study is seeking real-world data, part of the participants' safety data will be collected retrospectively by the Investigator or designee. This means that, following the initial capture of information in the eDiary/memory aid by the parents or LARs, the Investigator or designee will be seeking additional or missing participant data from the medical facility where the medical visit or the hospitalization occurred to complete the corresponding eCRF.

All SAEs will be recorded and reported to the Sponsor or designee immediately and under no circumstance should this exceed 24 hours, as indicated in Appendix 10.2. The investigator will submit any updated SAE data to the Sponsor within 24 hours of it being available.

Investigators are not obligated to actively seek information on AEs or SAEs after conclusion of the study participation. However, if the investigator learns of any SAE, including a death, at any time after a participant has been discharged from the study, and he/she considers the event to be reasonably related to the study intervention or study participation, the investigator must promptly notify the Sponsor.

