10.2.1 Definition of AE

AE Definition

- An AE is any untoward medical occurrence in a clinical study participant, temporally associated with the use of study intervention, whether or not considered related to the study intervention.
- NOTE: An AE can therefore be any unfavorable and unintended sign (including an abnormal laboratory finding), symptom, or disease (new or exacerbated) temporally associated with the use of study intervention.

Events Meeting the AE Definition

- Any abnormal laboratory test results (hematology, clinical chemistry, or urinalysis) or other safety assessments (eg, electrocardiograms, radiological scans, vital signs measurements), including those that worsen from baseline, considered clinically significant in the medical and scientific judgment of the investigator (ie, not related to progression of underlying disease).
- Exacerbation of a chronic or intermittent pre-existing condition including either an increase in frequency and/or intensity of the condition.
- New conditions detected or diagnosed after study intervention administration even though it may have been present before the start of the study.

- Signs, symptoms, or the clinical sequelae of a suspected intervention-intervention interaction.
- Signs, symptoms, or the clinical sequelae of a suspected overdose of either study intervention or a concomitant medication. Overdose per se will not be reported as an AE/SAE unless it is an intentional overdose taken with possible suicidal/self-harming intent. Such overdoses should be reported regardless of sequelae.

Events NOT Meeting the AE Definition

LRTI hospitalizations of any cause, including RSV LRTI hospitalization, occurring at any time post-dosing/randomization, will not be considered and reported as SAEs (see Section 8.3.1 for more information).

- Any clinically significant abnormal laboratory findings or other abnormal safety assessments which are associated with the underlying disease, unless judged by the investigator to be more severe than expected for the participant's condition.
- Medical or surgical procedure (eg, endoscopy, appendectomy): the condition that leads to the procedure is the AE.
- Situations in which an untoward medical occurrence did not occur (social and/or convenience admission to a hospital).
- Anticipated day-to-day fluctuations of pre-existing disease(s) or condition(s) present or detected at the start of the study that do not worsen.

Other Definitions

Adverse Reaction:

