5.1.2. Screening Period

For all participants, the screening period is defined as the period from informed consent to Day 1. For some variables, data from more than one assessment within the screening period can be collected prior to randomization (for no intervention group) / immunization (for nirsevimab group).

The baseline value for a variable is therefore defined as the last non-missing value collected before Day 1 in the screening period.

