5.1.3. Treatment Period

At the time of Primary Analysis, the Treatment Period is defined as the period from the date / time of randomization (for no intervention group) / immunization (for nirsevimab group) up to and including:

- The cut-off date for the Primary Analysis,
- Lost to follow-up or consent withdrawal date, if participant is lost to follow-up or withdraws consent.

At the time of First Year Analysis, the Treatment Period is defined as the period from the date / time of randomization (for no intervention group) / immunization (for nirsevimab group) up to and including:

- The date of 12-month safety follow-up call, if 12-month safety follow-up call occurs before or on Day 1 + 365 + 14,
- Day 1 + 365 + 14 date, if 12-month safety follow-up call occurs after Day 1 + 365 + 14,
- Lost to follow-up or consent withdrawal date, if participant is lost to follow-up or withdraws consent.

At the time of Second Year Analysis, the Treatment Period “from Day 1 to 366 Days Post-Dosing/Randomization” for UK reconsented participants is defined as the period from the date / time of randomization (for no intervention group) / immunization (for nirsevimab group) up to and including:

- The date of 12-month safety follow-up, if 12-month safety follow-up call occurs before or on Day 1 + 365 + 14,
- Day 1 + 365 + 14 date, if 12-month safety follow-up call occurs after Day 1 + 365 + 14
- The date of 24-month safety follow-up or until lost to follow-up or consent withdrawal

At the time of Second Year Analysis, the Treatment Period “from 366 Days Post-Dosing/Randomization to 731 Days Post-Dosing Randomization” for UK reconsented participants who are not lost to follow-up or who don’t withdraw consent before 366 Days Post-Dosing/Randomization is defined as the period from:

- The date of 12-month safety follow-up + 1, if 12-month safety follow-up call occurs before or on Day 1 + 365 + 14,
- Day 1 + 365 + 14 + 1 date, if 12-month safety follow-up call occurs after Day 1 + 365 + 14

Up to and including:

- The date of 24-month safety follow-up call, if 24-month safety follow-up call occurs before or on Day 1 + 730 + 14,
- Day 1 + 730 + 14 date, if 24-month safety follow-up call occurs after Day 1 + 730 + 14,
- Lost to follow-up or consent withdrawal date, if participant is lost to follow-up or withdraws consent.

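### SAP 6.7.2.1 can report an event that began before dosing as treatment-emergent without any worsening, and as treatment-related in the nirsevimab arm when causality is missing

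*SAP*

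**What the plan says.** SAP 6.7.2.1 sorts each AE on the eCRF into pre-treatment or treatment-emergent. An event that starts within the Treatment Period is a TEAE. An event that starts earlier becomes a TEAE only if two conditions both hold: it is one "whose severity is greater than 1 or missing", and its "stop date is missing or not before the Treatment Period". An earlier-onset event that is still open stays pre-treatment when it has a late or absent stop date "but with a grade lower or equal to 1".

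Under SAP 5.1.3 the Treatment Period begins at randomization in the no-intervention arm and at immunization in the nirsevimab arm. Before that, under SAP 5.1.2, "the screening period is defined as the period from informed consent to Day 1".

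On causality, SAP 6.7.2.1 calls a TEAE treatment-related if the investigator judged it so, or if it is one "with unknown / missing relationship to treatment for participants who received nirsevimab on Day 1". In no-intervention participants a missing relationship counts as not related. Neither rule refers to onset date.

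The protocol bears on this in four places:
- Section 10.2.1 counts the exacerbation of a pre-existing condition, in frequency or intensity, as an AE. It excludes expected fluctuations of conditions "present or detected at the start of the study that do not worsen".
- Section 10.2.3 includes onset before immunization in its definition of not related.
- Section 10.2.5 assigns one intensity grade to each AE.
- Section 8.3.2 says "Non-serious adverse events will be collected from dosing/randomization (D01) until 30 days after immunization".

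**The concern.** Treatment emergence should depend on when an event began or whether it got worse. For earlier-onset events the SAP uses the absolute grade instead, so a grade 2 event that was the same before and after the injection is reported as having emerged on treatment.

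The causality default then adds a one-sided step. A pre-dose event with a blank relationship field becomes treatment-related if the infant received nirsevimab and not related if the infant was in the control arm, although the protocol's own definition makes it not related.

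At stake are the safety tables built on these flags: the TEAE overview and the maximum-intensity, relationship and treatment-related tables of SAP 6.7.2.2, with their repeats by country, weight and age. SAP 6.9 also plans lay outputs on related TEAEs that are presented as side effects, so an event that preceded the injection could be shown to the public as a side effect of it.

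**Working it through.** No sample size, power or alpha is involved. The check is to apply the SAP's rules to every possible pattern and compare the results with the protocol.

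**Step 1. Events with onset before the Treatment Period, by recorded grade and stop date (SAP 6.7.2.1).**

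| Recorded grade | Stopped before Treatment Period | Stopped later | No stop date |
|---|---|---|---|
| 1 | pre-treatment | pre-treatment | pre-treatment |
| 2 | pre-treatment | TEAE | TEAE |
| 3 | pre-treatment | TEAE | TEAE |
| missing | pre-treatment | TEAE | TEAE |

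Six of the 12 cells are TEAEs. All six are events still open at the start of the Treatment Period. Events already over are pre-treatment at every grade.

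**Step 2. Open events, by course.** Assume that the one recorded grade is the highest reached.

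| Grade before dosing → highest grade | Worsened? | SAP class |
|---|---|---|
| 1 → 1 | no | pre-treatment |
| 1 → 2 | yes | TEAE |
| 1 → 3 | yes | TEAE |
| 2 → 2 | no | TEAE |
| 2 → 3 | yes | TEAE |
| 3 → 3 | no | TEAE |

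The rule agrees with a worsening test in four of the six courses. It disagrees for the two unchanged courses, 2 → 2 and 3 → 3. The recorded grade cannot separate them from the worsened ones: a recorded 2 may be 1 → 2 or 2 → 2, and a recorded 3 may be 1 → 3, 2 → 3 or 3 → 3.

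**Step 3. Relatedness of a TEAE, by arm.**

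| Recorded relationship | Nirsevimab recipient | No intervention |
|---|---|---|
| related | related | related |
| not related | not related | not related |
| missing | related | not related |

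The arms differ only in the last row. For an event with pre-dose onset, Protocol 10.2.3 gives not related in that row for both arms.

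**Step 4. Together.** Four things must coincide for a pre-dose event to become related through the default: onset before immunization, still open at immunization, grade above 1 or missing, and relationship missing. No rule in the SAP blocks that combination.

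**Step 5. Can such events arise?** Yes, but several provisions make them rare.
- The Schedule of Activities allows consent before Visit 01, so the screening period can last longer than a day. The SAP itself provides for pre-treatment AEs.
- Against that, non-serious AE collection starts at dosing/randomization (Protocol 8.3.2), and clinically relevant prior conditions go to medical history (Protocol 8.2.1). Exclusion E08 keeps out infants with moderate or severe acute illness on the dosing day.
- AEs starting on Day 1 are assigned to the Treatment Period (SAP 5.1.3), and incomplete start dates are imputed towards it (SAP 5.2.3.2). What remains is essentially events whose recorded dates place onset before Day 1.

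No passage gives a count or rate for these.

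**The case against.** The strongest defence is that the grade cut-off is a conservative proxy. With one grade per AE, a recorded grade of 1 cannot hide a rise in grade, while a recorded 2, 3 or blank might. Moving all such events to pre-treatment could hide real worsening. This stands as a reason why a flag for increased grade cannot simply be programmed from the data described. It does not make the proxy accurate (step 2), and it does nothing for the causality default.

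A second defence is that the protocol filters these events first: a known condition that does not worsen is not an AE and should not reach the derivation. That limits the number. It is also why Protocol 8.3.2 and 10.2.1 are better read as restricting the problem than as flatly contradicted by the SAP. The conflict with 10.2.3 is direct.

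A third is that investigators must document causality for every AE (Protocol 10.2.3), and that missing means not related in controls because they received no product. Both points are fair. Neither explains why the default should override an onset date that already settles the question.

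Stronger readings are tempting, but the documents do not support them:
- A reader might infer that every earlier event above grade 1 becomes a TEAE. The stop-date condition rules that out.
- A reader might infer a general bias against nirsevimab in the AE tables. The TEAE rule is the same in both arms; only the missing-relationship default is one-sided.
- A reader might infer that severe rows are inflated at grades 2 and 3 and by ungraded events. Protocol 10.2.2 equates severe with grade 3, and SAP 6.7.2.2 leaves ungraded events out of the intensity counts.
- A reader might attach a number. Assuming 0.1% to 0.5% of about 14 430 infants per arm gives 0.001 × 14 430 ≈ 14 to 0.005 × 14 430 ≈ 72. Nothing in the documents supports that rate, and the figure would include events that did worsen.

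**Conclusion.** The rule is wrong as written, with probably small impact. Two parts hold on the text alone. The causality default ignores onset date and so conflicts with Protocol 10.2.3, in one arm only. The TEAE rule admits unchanged grade 2 and 3 events and ungraded events that began before dosing, which fits poorly with Protocol 10.2.1.

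The number affected cannot be derived from the documents. The judgement that it is small assumes that sites follow the collection window and record prior conditions as medical history. AEs are not compared statistically between arms, and the AE listing flags treatment emergence and gives relative start day for dosed infants, so an affected nirsevimab event could be found there. No efficacy conclusion is touched.

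**What to change.** 1. **Causality default.** In SAP 6.7.2.1, apply the rule that missing or unknown counts as related only to events with onset on or after immunization, in line with Protocol 10.2.3.

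2. **Treatment emergence.** Define a TEAE by onset on or after randomization/immunization. A post-dose exacerbation of an earlier condition is an AE under Protocol 10.2.1 and should be entered as its own event with its own onset date. Earlier-onset events are listed as pre-treatment whatever their grade. Protocol 10.2.1 also counts a condition first detected after administration even if it was present before, so the SAP should say which date is its onset.

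3. **If the grade rule is kept** because only one grade is collected, report the number of TEAEs with pre-dose onset by arm, and show the TEAE tables with those events removed. The same count would settle the impact on any tables already produced.

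The cost is SAP wording and a derivation based on dates already collected. The downside of item 2 is that a worsening not entered as a separate AE would appear only in the pre-treatment listing. Item 3 avoids that loss but leaves the main tables as they are.
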